10.3.6.2 Analysis and declaration of other safety data

This relates to any safety data or new fact that could significantly alter the assessment of the benefit-risk ratio for the experimental medication, or for the research, or which could lead to the possibility of altering the administration of the experimental medication or altering the conduct of the research.

New facts must be declared to the competent authorities within 15 calendar days of the sponsor becoming aware. Additional relevant information must be sent within an additional 8 days after the 15-day deadline.

10.3.6.3 Annual safety report

Once a year for the duration of the clinical trial, the sponsor must draw up an annual safety report (Development Safety Update Report - DSUR) which includes, in particular:

- an analysis of the safety of the research subjects
- a description of the patients included in the trial (demographic characteristics, etc.)
- a line listing of suspected serious adverse reactions that occurred during the period covered by the report
- a cumulative summary tabulation of serious adverse events that have occurred since the start of the research

The report must be delivered no later than 60 days after the anniversary of the date on which the ANSM authorised the trial.

10.3.7 Data Safety Monitoring Board

The Data and Safety Monitoring Board (DSMB) can be established by the sponsor. Its primary mission is to serve as a committee for monitoring safety data. It can have other missions, such as monitoring efficacy data (especially if the protocol includes interim analyses).

The DSMB is mentioned in Article L. 1123-7 of the French Public Health Code.

The sponsor is responsible for justifying the creation or absence of a supervisory committee to the Competent Authority (ANSM) and to the CPP.

A DSMB will be convened for this biomedical research. The members of the DSMB will be named after the research starts. During the first meeting of the DSMB, a chairman will be appointed and the members will determine their operating methods and the meeting schedule. All missions as well as the precise operating methods of the DSMB will be described in the DSMB's charter for the research.

General information about the DSMB

The DSMB makes recommendations to the sponsor about the continuation, modification or termination of the research upon interim analysis. The recommendations that the DSMB can make are:

- to continue the research with no modifications
- to continue the research with a modification to the protocol and/or to the monitoring of subjects
- to temporarily halt inclusions
- to permanently terminate the research in light of:
 - o safety data: serious adverse reactions
 - o efficacy data: proven futility or efficacy

The DSMB is appointed by the sponsor and is made up of at least 3 people with no connection to the research, including at least one clinician specialising in the pathology being studied and one specialist in the medication being studied (or a pharmacologist/pharmacovigilance specialist), and possibly a methodologist/biostatistician, particularly in the case of interim analysis.

The DSMB has a consultative role in advising the sponsor on safety issues such as tolerance and re-assessment of the benefit-risk ratio during the research.

The DSMB must hold its preliminary meeting before the first inclusions of the first subject and ideally before the protocol is submitted to the competent authority and the CPP. The committee's agenda will be as follows:

Definition of the DSMB's missions:

- Validation of the research methodology:

The proposed methodology for the clinical trial will be validated by the DSMB so that it does not jeopardise the safety of subjects, in particular relating to the inclusion and randomization methods.

- Validation of tolerance monitoring methods:
 - o nature of the evaluated parameters
 - o frequency of the evaluations, consultation schedule
- Validation of termination criteria:
 - o criteria for terminating a subject's participation for tolerance reasons

- criteria for the temporary or permanent termination of the research (leading to the establishment of certain recommendations ("stopping rules"))
- Modification of the protocol and recommendations:
In light of the analysis of tolerance data for the research, the DSMB can, when applicable: propose substantial modifications in order to modify certain data, in particular relating to the protocol (inclusion and non-inclusion criteria, monitoring, additional exams, etc.). Likewise the DSMB can issue any recommendations it deems useful in order to best ensure the safety of the research subjects and to maintain a favourable benefit-risk balance throughout the research.

Definition of the DSMB's operating methods:

- meeting types (open session, then closed sessions) and schedule
- desired methods and format of SAE notification from the sponsor to the DSMB

The DSMB appoints its chairman at the first meeting.

The sponsor retains decision-making authority. When applicable, the sponsor delivers its decision, with justification, and DSMB reports to the Competent Authority (ANSM) and the CPP.

11 DATA MANAGEMENT

11.1 Data collection methods

Study data will be collected and managed using REDCap electronic data capture tools hosted at Centre Hospitalier Sainte-Anne. REDCap is a secure, web-based software platform designed to support data capture for research studies, providing 1) an intuitive interface for validated data capture; 2) audit trails for tracking data manipulation and export procedures; 3) automated export procedures for seamless data downloads to common statistical packages; 4) procedures for data integration and interoperability with external sources.

11.2 Identification of data collected directly in the CRFs and that will be considered as source data

Patients will be identified through their initials, number center and randomization number.

11.3 Right to access source data and documents

11.3.1 Access to data

In accordance with GCPs:

- the sponsor is responsible for obtaining the permission of all parties involved in the research to guarantee direct access to all locations where the research will be carried out, to the source data, to the source documents and the reports, with the goal of quality control and audit by the sponsor
- the investigators will make available to those in charge of monitoring, quality control and audit relating to the biomedical research the documents and personal data strictly necessary for these controls, in accordance with the legislative and regulatory provisions in force (Articles L.1121-3 and R.5121-13 of the French Public Health Code)

11.3.2 Source documents

Source documents are defined as any original document or object that can prove the existence or accuracy of a piece of information or a fact recorded during the research. These documents will be kept for 15 years by the investigator or by the hospital in the case of a hospital medical file. Electronic Health record and Radiological reports will be kept by the investigators of each centre

11.3.3 Data confidentiality

Those responsible for biomedical research quality control (Article L.1121-3 of the French Public Health Code) will take all necessary precautions to ensure the confidentiality of information about the experimental medications, the research, the research subjects and in particular the identity of the subjects and the results obtained.

These individuals, as well as the investigators themselves, are subject to professional secrecy (in accordance with the conditions set out in Articles 226-13 and 226-14 of the Penal Code). During or after the biomedical research, the data collected about the research subjects and sent to the sponsor by the investigators (or any other specialised parties) will be made non-identifying.

Under no circumstances should the names and addresses of the subjects involved be shown. The sponsor will ensure that each research subject has given permission in writing for access to personal information about him or her which is strictly necessary for the quality control of the research.

11.3.4 Data security

11.3.4.1 Measures Implemented Upstream:

- Presence of a full-time Data Protection Officer (DPO) and Chief Information Security Officer (CISO) internally;
- Raising awareness among employees about personal data protection (both in paper and digital formats), privacy, and cybersecurity;
- Confidentiality and IT tool usage charters in place and signed by all employees, partners, and service providers;
- Established Information Security Policy (PSSI);
- Regular IT system audits and remediation of any identified risks;
- Cybersecurity aspects :
 - Securing remote access via VPN + MFA,
 - TLS access for web applications,
 - Pseudonymization and encryption of data,
 - Segmentation (separating web sections from databases),
 - Logical access control through ID+Password authentication, with deactivation of unused accounts after 3 months,
 - Account blocking after multiple failed login attempts,
 - Securing IT communication channels (firewall, traffic monitoring probes),
 - Inventory (CMDB) and hardware redundancy,
 - Access granted per project,
 - Securing operations: daily backup policy for VMs and servers, PSSI;
 - Data archiving policy preventing any subsequent modification or extraction;
 - Strict compliance with the principle of data minimization;
 - Protection against malware (XDR solution, DMZ servers, and traffic control).

11.3.4.2 Measures to Be Implemented in Case of a Data Security Breach to Mitigate Possible Negative Effects:

- Restoration of lost data via daily backups in case of loss of availability or unintended modification;
- Set of measures preventing the reuse of data in case of theft, interception, etc. (encryption through VPN + MFA + TLS access for web applications);
- Personal data breach management policy (notification of the incident to the CNIL, general and personal communication to affected individuals, etc.).

11.4 Data processing and storage of documents and data

11.4.1 Identification of the manager and the location(s) for data processing

The data management will be realized in the DRCI of GHU Paris Psychiatrie et Neurosciences with [name] and the statistical analysis will be done by [name].

11.4.2 Data entry

Data entry will be carried out on electronic media via a web browser connecting to the REDCAP server hosted at GHU Paris Psychiatrie et Neurosciences center

11.4.3 Data processing (CNIL, the French Data Protection Authority) in France

This research falls under the "Méthodologie de référence" (MR-001) according to the provisions of Article 54, paragraph 5 of modified Law No. 78-17 of 6 January 1978 relating to information technology, data files and privacy. This change was approved in a decision made on 5 January 2006. Le GHU Paris Psychiatrie et Neurosciences, the research sponsor, has signed a commitment to comply with this " Méthodologie de référence "

The processing of personal data for this research falls under the scope of the provisions of Articles 53 to 61 of the Law of 6 January 1978 relating to information technology, data files and privacy, modified by Law No. 0204-801 of 6 August 2004.

11.4.4 Archival

Specific documents for biomedical research relating to a medication for human use will be archived by the investigator and the sponsor for a period of 15 years after the end of the research.

This indexed archival includes, in particular:

- A sealed envelope containing the original copies of all information sheets and consent forms signed for all individuals at the centre that participated in the research for the investigator
- A copy of all the information notes and consent forms signed for all subjects at the centre that participated in the research for the sponsor
- "Research" binders for the Investigator and the sponsor, including:
 - the successive versions of the protocol (identified by the version no. and date), and the appendices
 - the ANSM authorisations and CPP favourable opinions

"CASH" protocol, version 2.1 of 04/04/2025

- letters of correspondence
- the inclusion list or register
- the appendices specific to the research
- the final research report
- The data collection documents

11.5 Ownership of the data

Le GHU Paris Psychiatrie et Neurosciences is the owner of the data, which cannot be used or disclosed to a third party without its prior approval.

12 STATISTICAL ASPECTS

12.1 Description of statistical methods to be used including the timetable for the planned interim analyses

CASH is a multicentre, double-blinded, randomised, placebo-controlled, parallel-group superiority trial in adult, using an adaptive group-sequential design, to demonstrate that cilostazol plus nimodipine is safe and superior to nimodipine alone will improve modified Ranking Score (mRS) at six months.

Two interim analyses for futility and efficacy are planned.

Populations

For the statistical analysis, the following populations are defined:

Population	Description
Intent-To-Treat (ITT) Population	The ITT population will include all randomised participants. ITT participants will be analysed according to the randomised treatment, regardless of the actual treatment received. All efficacy analyses will be performed on the ITT population.
Per Protocol (PP) Population	The PP population will include all participants in the ITT with at least 80% of doses received to define adherence to treatment. The PP population will be used for supportive analyses of efficacy measures.
Safety Population (SP)	The SP will include all randomised participants who received at least one treatment (active or placebo). The SP will be analysed according to the actual treatment received. This population will be used for safety analyses.

Description of the statistical methods, including the timing of planned interim analyses

The statistical analysis plan (SAP) will be developed and finalised before the database is locked.

Below is a description of the planned statistical analysis. Further details will be presented in the statistical analysis plan (SAP).

All statistical analyses will be performed with SPSS version 26 or RStudio. For analyses performed with RStudio, the script used will be provided.

The baseline is defined as the last evaluation performed before the start of the study treatment, day 1 (V1).

All data collected after the start of the study treatment are defined as post-baseline.

Baseline characteristics will be summarised by the treatment group. The mean and standard deviation (SD) or median and interquartile range (IQR) for skewed variables will be summarised for continuous measures.

The proportion in each category will describe categorical variables.

In addition, the 95% confidence interval (CI) will also be calculated as indicated.

All categorical variables will be summarised by treatment with numbers and percentages of participants.

All continuous variables, including changes from baseline, will be summarised by treatment with means, standard deviations or medians and interquartile range [IQR] for skewed variables.

The following formula will be used, depending on how the post-basal endpoint is defined, for each scheduled visit and for each time point at which both baseline and post-basal values are available:

- Change from baseline = post-baseline value - baseline value
- Percentage change from baseline = $(\text{post-baseline value} - \text{baseline value})/\text{baseline value} \times 100\%$
- Ratio to baseline = post-baseline value / baseline value

Primary objective

The analysis of clinical effectiveness will be performed on the ITT population.

For the assessment of the primary objective, the percentage of patients who responded to treatment per experimental arm will be evaluated. Specifically, treatment will be considered effective when mRS at six months is ≤ 2 .

Therefore, the treatment response variable will be dichotomised as follows

0 if the mRS is > 2 (non-responder patient)

1 if the the mRS value is ≤ 2 (responders).

A logistic regression model adjusted by centre, age (continuous), and severity at inclusion, considering the dichotomised value of the mRS (≤ 2 , > 2) as the response variable, and will be used. Consequently, the efficacy of the experimental treatment will be expressed as an adjusted Odds Ratio, and the 95% confidence interval and NNT index will be provided.

Sensibility analysis

The described analysis for the assessment of clinical efficacy will be repeated in the per-protocol population and after the replacement of missing data of mRS at six months, on the one hand, according to a "worst case scenario" logic and on the other hand, using multiple imputations.

Secondary efficacy analyses

Secondary analyses of clinical effectiveness will be performed on the ITT population. Analyses on per protocol population may be carried out.

A logistic regression model adjusted by centre, age (continuous) and severity at inclusion will be used considering the dichotomised mRS value at six months (≤ 1 versus > 1).

The time-to-event variables will be analysed using the Cox proportional hazards model, including randomisation arm, age (as a continuous variable), severity at inclusion, and centre as model terms. The hazard ratio between the arms will be presented with the 95% CI and p-value of the model. Kaplan-Meier curves will be presented by the arm for each appropriate endpoint.

For the primary objective, both overall and by subgroups, the following statistics will be provided: effect size, confidence intervals, number needed to treat and absolute risk reduction as appropriate.

All tests will be two-sided with a unilateral significance level of 0.025% adjusted for the interim analysis.

Subgroup analyses

Subgroup analyses will be performed to assess the consistency of the treatment effect between subgroups without multiplicity adjustment. The following subgroups will be assessed for the primary endpoint:

- Fisher grade I to III versus IV
- Age: <50 years; >=50 and <=70 years; >70 years

The treatment effect for the total population and subgroups will be represented using forest plot graphs.

For HR and OR in subgroup analyses, the significance of the interaction will be tested using the method proposed by Altman & Bland 2003.

Treatment of missing data

For the analysis of the primary endpoint, in the event of study exit prior to evaluation of the primary endpoint (6 months), the last recorded mRS value will be used (LOCF method, mRS at ICU discharge) patients will be considered as non responders if no mRS are recorded.

For all other variables, in case of a significant proportion of missing data (>10% of subjects), a sensitivity analysis using multiple conditional imputation techniques by chained equations (MICE) will be performed, according to a conservative principle, using the mean severity at inclusion as the central position parameter and an estimate of the intra-patient variability in the placebo group as the dispersion parameter. Sensitivity analysis based on imputed data will be considered secondary.

Further details on the treatment of missing data will be provided in the SAP.

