In light of the results obtained for the sample size estimation, an OR between the two arms of 1.86 is assumed as a precaution. This assumption sets the proportion of patients who will obtain a favourable outcome in the control arm at 65% and the proportion of responders in the experimental arm at least 76%. These proportions may appear high, but it should be noted that the study does not include patients with early death and without surgery.

The experimental design includes two intermediate analyses; a sequential group test and the O'Brian-Fleming Analog spending function for alpha and beta errors were used.

Therefore set unilateral alpha at 0.025 and the power of the test (1-beta) at 0.80, 284 patients are needed per experimental arm; details are given in table 3 and figure 1.

A drop-out rate of no more than 10% is expected so that the sample size will be 630 patients (315 per experimental arm).

All estimates for the interim analyses are made without considering the inflation quota for drop-out patients. Therefore this evaluation will be made at the planned number of patients who completed the study. Only the final analysis will bear any inflationary share of the sample.

Table 3. Summary Report -

Item	Value
Maximum Number of Stages (Design):	3
Current Stage:	0
Alternative Hypothesis:	$P1 - P2 < 0$ (one-sided)
Alpha Spending Function:	O'Brien-Fleming Analog
Beta Spending Function:	O'Brien-Fleming Analog
Futility Boundaries:	Binding
Target Alpha:	0.025
Alpha (from simulations):	0.025
P1:	0.65
P2:	0.76
N1 (if final stage reached):	284
N2 (if final stage reached):	284
Target Power:	0.8
Power (from simulations):	0.8016
Maximum Information:	692.8

Information Report

Maximum Information: 692.8519

 Alternative Hypothesis: $P1 - P2 < 0$ (one-sided)

Alpha: 0.0250

Stage	Target information proportion	Target sample size N1	Target sample size N2	P1	P2
1	0.33	95	95	0.65	0.76
2	0.67	189	189	0.65	0.76
3	1.00	284	284	0.65	0.76

Alpha Spending

Target Final Stage Alpha: 0.0250

Spending Function: O'Brien-Fleming Analog

Stage	Information proportion	Alpha spent this stage	Cumulative alpha spent	Percentage alpha spent at this stage	Cumulative percentage
1	0.33	0.0001	0.0001	0.4	0.4
2	0.67	0.0059	0.0060	23.8	24.2
3	1.00	0.0190	0.0250	75.8	100.0

Beta Spending for Futility

Target Cumulative Beta at Final Stage: 0.2000

Spending Function for Futility: O'Brien-Fleming Analog

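### Section 12.1 gives a self-contradictory test level of 0.025%, 100 times smaller than the one-sided 0.025 on which the design is built; the design itself is unaffected

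*Protocol*

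**What the plan says.** Section 12.1, in the text on secondary efficacy analyses, states: "All tests will be two-sided with a unilateral significance level of 0.025% adjusted for the interim analysis". It is the only sentence in 12.1 that sets a test level, and its scope is every test, so it reaches the primary endpoint too.

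Section 12.5 states the design level differently: "Therefore set unilateral alpha at 0.025 and the power of the test (1-beta) at 0.80, 284 patients are needed per experimental arm". Table 3 there gives a target alpha of 0.025 and "Alternative Hypothesis: $P1 - P2 < 0$ (one-sided"). The alpha-spending table is headed "Target Final Stage Alpha: 0.0250" and accumulates 0.0001, 0.0060 and 0.0250 over the three looks. On the method, 12.5 says that "a sequential group test and the O'Brian-Fleming Analog spending function for alpha and beta errors were used". The efficacy limits are z = -3.7103, -2.5111 and -1.9308. Section 12.7 repeats the first two, rounded, as the interim stopping rules and uses -1.9308 for the last look.

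**The concern.** The sentence has two separate faults.

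1. **Level.** A percent sign turns 0.025 into 0.00025. No other part of the protocol uses that value.
2. **Sidedness.** The tests are called two-sided and the level one-sided. Deleting the percent sign leaves this open. The sentence could then mean 0.025 in each tail, or a two-sided p-value compared with 0.025, which is 0.0125 in each tail.

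The sentence states the threshold for declaring success, so it is part of the decision rule. Sidedness can matter at the margin. A result exactly on the final limit of 1.9308 has a one-sided nominal p of 0.0268 and a two-sided p of 0.0535. It would count as success under the printed limit while the two-sided p-value exceeds 0.05, and the wording of 12.1 could be cited for either conclusion. Two interim efficacy looks are planned, and a correction made after one of them could look data-driven.

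**Working it through.** **Inputs (section 12.5).** Favourable outcome 65% on control and 76% on cilostazol; 284 per arm; looks at 95, 189 and 284 per arm; one-sided alpha 0.025; power 0.80; efficacy limits |z| = 3.7103, 2.5111, 1.9308; binding futility.

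**Step 1: does one-sided 0.025 reproduce the design?**

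- Variance term: 0.65 × 0.35 + 0.76 × 0.24 = 0.2275 + 0.1824 = 0.4099. Maximum information: 284 / 0.4099 = 692.85, as printed.
- Spending function: 2 × [1 − Φ(z(1 − α/2) / √t)] with α = 0.025, so z = 2.2414. At t = 1/3 this gives 0.0001, at t = 2/3 it gives 0.0060, and at t = 1 it gives 0.0250. All three match the table.
- Simulation of the three looks with the limits printed in 12.5 (normal increments, 3 million runs): type I error 0.0250, power 0.803. A direct binomial simulation (1 million runs): type I error 0.0251, power 0.800. The protocol reports 0.025 and 0.8016.

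The design is therefore internally consistent at one-sided 0.025. These runs used the second-look futility limit of -1.1224 from 12.5. Section 12.7 prints -1.224, and with that value type I error is 0.0241 and power 0.794. That mismatch is a separate matter and does not affect the efficacy limits.

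**Step 2: compare the level in 12.1 with the design.**

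- 0.025% = 0.00025, and 0.025 / 0.00025 = 100.
- Cumulative alpha at the second look: 0.0060 / 0.00025 = 24.

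| Look | Efficacy limit | Nominal one-sided p | Compatible with 0.00025? |
|---|---|---|---|
| 1 | -3.7103 | 0.0001 | yes, taken alone |
| 2 | -2.5111 | 0.0060 | no |
| 3 | -1.9308 | 0.0268 | no |

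**Step 3: what would literal use of the sentence do?** Take a single final test at 284 per arm.

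- Noncentrality: 0.11 / √(0.4099 / 284) = 0.11 / 0.03799 = 2.895.
- Power = Φ(2.895 − critical z).

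| Level applied | Critical z | Power |
|---|---|---|
| one-sided 0.025 (the design level) | 1.960 | 82.5% |
| two-sided 0.025 (0.0125 per tail) | 2.241 | 74.3% |
| one-sided 0.00025 | 3.481 | 27.9% |
| two-sided 0.00025 | 3.662 | 22.2% |

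With a pooled variance under the null, the last two rows become 27.1% and 21.4%. The single-test benchmark is 82.5%; the protocol's 80% belongs to the three-look design.

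**The case against.** The strongest defence is that the intended level is not in doubt. Section 12.5 states it in the text, in Table 3 and in the spending table, and the interim decisions in 12.7 are written as z limits, with no reference to the sentence in 12.1. This stands. A reader might infer from the sentence that the trial has only 22% to 28% power. The documents do not support that: nothing else uses 0.00025, it cannot operate alongside the second and final limits, and the design keeps its power of about 80%.

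A second defence is that the phrase on sidedness has a natural meaning: two-sided tests with 0.025 in each tail. That fits the 95% confidence intervals called for in 12.1, and its efficacy tail equals the one-sided 0.025 of 12.5. It is a fair guess at the intent. It still requires the percent sign to be ignored, and it does not sit with the one-sided alternative in Table 3, so the wording needs repair.

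A third concerns the secondary tests. A reader might infer that their sidedness is wholly undefined, or that they should be tested two-sided at 0.05 without interim adjustment. Neither follows. The sentence does call all tests two-sided, and it does apply an interim adjustment to all of them. What is unclear is the level, and what that adjustment means for endpoints that have no stopping limits. Statisticians may differ on the right choice, so the sponsor has to make it.

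**Conclusion.** The sentence is wrong as written: contradictory on sidedness, and a factor of exactly 100 away from the alpha that the design uses. Because it states a decision threshold for all tests, it should be corrected even though the intended primary level can be recovered from 12.5. The error is confined to this sentence. Sample size, spending table, efficacy limits and the stated 80% power all stand.

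The power figures of about 28% and 22% describe only literal use of 0.00025 in a single final test, assuming 284 evaluable patients per arm, rates of 65% and 76%, and a normal approximation to the unadjusted comparison of proportions. They are not an expected loss. Only the protocol is at hand, so nothing can be said about whether the SAP carries the same wording.

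**What to change.** Replace the sentence in 12.1 with one along these lines: *The primary endpoint will be tested at an overall one-sided alpha of 0.025 (2.5%), using the O'Brien-Fleming-type spending limits printed in sections 12.5 and 12.7.*

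Add a short statement, with the sponsor's choice, that gives one sidedness and one level for the secondary tests and says whether the interim adjustment applies to them.

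The cost is one replaced sentence and one added statement in the protocol. No sample size, spending figure or efficacy limit has to be recalculated. It should be done before the first interim analysis, planned at 190 completed patients, so that the threshold is settled before any efficacy look.
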